Once recruited to the study and after baseline measures are taken at T0 by the study coordinator, the randomization will be performed. Since study groups will be subdivided by gender, separate randomization will be performed for males and females. Block randomization will be used. Based on gender, 20 opaque envelopes will be generated containing the group allocation (10 for the vibration study group, 10 for the non-vibration control group). At the time of randomization, the

subject will choose an envelope and disclose the group assignment. For subjects allocated to the vibration group, the study coordinator will provide detailed instructions as to how to operate the appliance and will instruct those subjects to use it for 20 minutes per day.

Timetable of Study Assessments

Assessment/ Visit	Screen	Baseline T0	Visit T1	Visit T2	Visit T3
Week	2d-to -6w	0	5-6	10-12	15-17
Consent	X				
Inclusion Criteria/ Confirm	X	X			
Alginate Impression		X	X	X	X
Randomization *		X			
Braces applied /bonded		X			
Vibration Appliance instructions**		X			
Saliva Collection		X	X	X	X
Clinical Data		X	X	X	X
Periotest		X	X	X	X
Pain Diary*** & OHIP 14		X	X	X	X***
Model Analysis		X	X	X	X
Record Adverse Effects		X	X	X	X

*Randomization before bonding

**For vibration group only- SC initially provides device and manufacturer's instructions.

*** Diary provided @ Baseline & visit T1, T1 to be collected on next visit.

III. Data Collection Procedures (See Study Timetable)

On the day of bonding (T0), prior to the placement of any appliances, baseline unstimulated whole saliva will be collected and Periotest will be performed on selected teeth in the mandibular arch. In addition, alginate model impressions will be taken. These procedures will be described in more detail in the next sections. Once baseline measures have been taken, the PI will perform the randomization and notify the study coordinator as to which group the subject is assigned to ("vibration treatment" or "no vibration"). The patients allocated to the vibration treatment group

will be provided with the AcceleDent appliance and instructed to use the 20 minutes per day according to the manufacturer's instructions.

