After fixed appliances are placed and tooth movement begins, subjects will proceed with standard orthodontic treatment with or without vibration treatment based on allocation. Collection of saliva samples, Periotest and alginate impressions will be taken at T1 (5-6 weeks post-T0), T2 (10-12 weeks post-T0) and T3 (15-17 weeks post-T0). Subjects will be seen between noon and 5pm to help minimize possible confounding of salivary markers by circadian rhythms.

Salivary Biomarkers

Collection of unstimulated whole saliva will be performed using the same methods described by Navazesh and Kumar⁴⁸:

"The patient is advised to refrain from intake of any food or beverage (water exempted) one hour before the test session. Smoking, chewing gum and intake of coffee also are prohibited during this hour. The subject is advised to rinse his or her mouth several times with deionized (distilled) water and then to relax for five minutes.

The patient is then told the following: "I will first obtain measures of saliva flow while you are at rest. This means that before and during the collection you should make every effort to minimize movement, particularly movements of your mouth. To begin a collection trial, I will ask you to swallow to void the mouth of saliva. Then you should lean your head forward over the test tube and funnel" (demonstrate). "Keep your mouth slightly open and allow saliva to drain into the tube. Keep your eyes open. At the end of the collection period, I will ask you to collect any remaining saliva in your mouth and spit it into the test tube. This movement should be done very quickly and should be done in the same manner from trial to trial. This is very important. Do you understand the procedures?"

When you start a trial, tell the subject:

1. *Swallow to begin a trial (begin timing).*
2. *Make as little movement as possible. Do not swallow, and keep your eyes open during collection periods.*
3. *At the conclusion of the trial, collect the remaining saliva and spit it out."*

Unstimulated whole saliva will be collected by passive drooling into sterile centrifuge tubes on ice for 15 minutes or once 2-10mL of saliva is collected at baseline and each visit, whichever occurs

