Two blinded clinical evaluators will assess the rate of alignment of the lower incisors for both groups. Analyses of dental casts will be done on the mandibular cast using a method based on Little's irregularity index. Little's irregularity index was developed to assess amount of anterior tooth displacement from canine to canine (see Cast Irregularity Data Collection Form). Contact displacement will be measured in millimeters around the arch from canine to canine. Irregularity will be measured on models from each of the four time points and be evaluated based on percentage change over the 6-month evaluation period.

Orthodontic Pain Assessment

Subjects will be given a pain diary on the baseline (T0), visits T1 & T2 to record the level of orthodontic pain each evening for the first 7 days after each study visit. The degree of pain will be assessed using a Visual Analog Scale (VAS) ranging from 1 (least pain) to 10 (highest pain)⁵⁴. In addition, patients will report if the pain is constant or only present on biting/chewing⁵⁵. The subjects will return the completed diary to the next visit to be collected by the study coordinator and kept in the study record.

Oral Health Quality of Life (OHQoL)

To assess the impact of the vibration appliance on the overall oral health quality of life of the subject, subjects will be given an Oral Health Impact Profile (OHIP-14) questionnaire⁵⁶. The OHIP-14 consists of 14 questions divided into specific dimensions including functional limitation, physical pain, psychological discomfort, physical disability, psychological and social disability and overall life handicap from orthodontic treatment with or without the vibration appliance. The OHIP-14 (exhibit below) will be administered at each study visit and the profile changes will be compared across time points in data analyses.

OHIP-14 Questionnaire:

Dimension	Question	Weight
Functional Limitation	Have you had trouble pronouncing any words because of problems with your teeth or mouth?	0.51
	Have you felt that your sense of taste has worsened because of problems with your teeth or mouth?	0.49
Physical Pain	Have you had painful aching in your mouth?	0.34
	Have you found it uncomfortable to eat any foods because of problems with your teeth or mouth?	0.66
Psychological Discomfort	Have you been self-conscious because of your teeth or mouth?	0.45

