The timing of visit activity is planned to coincide with normally scheduled clinic provider/patient visits. Typically, treatment for non-extraction cases last from 12-30 months in the Orthodontic clinic using fixed appliances. However, the subjects will only be evaluated during the first 6 months of their clinical appliance treatment for the study purpose and data. Providers will follow patients every 5-6 weeks and the study coordinator will ensure/confirm the patients for study appointments per Timetable, pg. 9. After completion of the observation and data collection phase (up to 17 weeks), the patients will continue to proceed with treatment as directed by the their primary orthodontic provider. Data collection will occur at normally scheduled visits with no additional appointments specific to the study.

In the event that the PI determines that a subject is not suited to continue in the study (eg. the subject shows consistent failure to keep appointed visits, consistent breakage of appliances, patient safety considerations, etc.) he/she will be withdrawn by the PI from the study and no further data will be collected. Specifically, poor compliance with attending appointments during the allotted time frame for each study visit will result in subjects being disqualified from the study. For example, the follow-up time frame for T1 is 5-6 weeks after T0 (baseline). Therefore if the patient misses an appointment and cannot or does not reschedule to attend his/her appoint during the allotted time from (by 6 weeks after T0), then he/she will be disqualified from the study. Also, in the event of bracket breakages (as stated earlier), the subject is to be seen within 7 days to have the bracket rebounded. The primary orthodontic provider will reposition the bracket in the ideal position and continue with alignment using the study archwires. If the subject does not present with 7 days of the breakage, he/she will be disqualified from the study.

The data collected to that point will be utilized in analyses. The patient's treatment will continue with the primary orthodontic provider consistent with the standard of care.

VI. Statistical/Data Analysis

Intra and inter-rater reliability of the irregularity measurements will be assessed using the T0 and T3 models evaluated by the two blinded evaluators one week apart for all patients. A Cronbach alpha analysis will be used to assess reliability of the measurements. A single calibrated evaluator

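### Each pain diary covers seven evenings but is collected only at the next study visit, so the plan has no provision for one finished before disqualification and leaves weeks open to recall entry

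*Combined protocol and SAP*

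**What the plan says.** **Recording.** Section III, Orthodontic Pain Assessment, names three diaries: "Subjects will be given a pain diary on the baseline (T0), visits T1 & T2". Each diary spans the seven evenings that follow its visit, and each entry is a VAS rating.

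**Return.** The same paragraph: "The subjects will return the completed diary to the next visit to be collected by the study coordinator and kept in the study record". The footnote to the Timetable of Study Assessments also has collection at the next visit, but names fewer diaries: "Diary provided @ Baseline & visit T1, T1 to be collected on next visit". Section V adds: "Data collection will occur at normally scheduled visits with no additional appointments specific to the study".

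**Leaving the study.** Section V says that "poor compliance with attending appointments during the allotted time frame for each study visit will result in subjects being disqualified from the study". It applies the same sanction to a subject who is not seen within 7 days of a bracket breakage. For a subject withdrawn by the PI it rules out gathering anything more, and it then says: "The data collected to that point will be utilized in analyses".

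**Analysis.** Section VI compares VAS between groups by a Wilcoxon rank sum test at α = 0.05. It has no rule for a late or missing diary.

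**The concern.** The information in a diary is complete one week after the visit, but the plan takes possession of it only weeks later, and only if the subject is still in the study. Two things are at stake.

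- **Loss.** A subject may record all seven evenings after bonding while fully in the study, then miss the T1 window. The ratings exist on paper, but no provision brings them into the study record. If T1 is missed, that subject could have no diary VAS score at all.
- **Recall.** A diary that stays at home for weeks after its last entry can be filled in shortly before the visit. Subjects know their arm: under section II they open the allocation envelope themselves, only one arm receives a device, and no sham is described. Late entries by unblinded subjects add noise, and possibly bias, to a self-reported outcome.

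The daily VAS is the main evidence for hypothesis 4 and aim 4. The background also says that pain over subsequent visits, to weeks 15-17, is what needs to be understood. The point concerns ratings already made before a subject leaves. It does not ask whether disqualified subjects should go on being measured.

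**Working it through.** The plan gives no power, effect size or dropout figure for pain, so there is no stated figure to reproduce. The check is of timing, then of size under an assumed rate.

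**1. Delay from last entry to hand-in.** Visit windows after T0 (section III): T1 at weeks 5-6, T2 at weeks 10-12, T3 at weeks 15-17. The last entry is on day 7 after the visit.

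Shortest delay = 7 × (earliest week of next visit − latest week of this visit) − 7 days. Longest delay = 7 × (latest week of next visit − earliest week of this visit) − 7 days.

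| Diary | Shortest | Longest |
|---|---|---|
| T0, returned at T1 | 7 × (5 − 0) − 7 = 28 days | 7 × (6 − 0) − 7 = 35 days |
| T1, returned at T2 | 7 × (10 − 6) − 7 = 21 days | 7 × (12 − 5) − 7 = 42 days |
| T2 (if issued), returned at T3 | 7 × (15 − 12) − 7 = 14 days | 7 × (17 − 10) − 7 = 42 days |

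**2. The rules side by side.** A subject disqualified for missing T1 leaves after week 6, which is 42 − 7 = 35 days after the last T0 entry. The only described collection point is the visit that was missed. Section V then bars further collection and analyses what was collected by then. It does not say on which side of that line a finished but unreturned diary falls.

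**3. Possible size.** The documents give no disqualification rate, so let q be the chance of disqualification in each interval between visits, taken as 5% to 15% (assumption). Suppose that each disqualification comes after day 7, that the diary was completed, and that it is not accepted afterwards. These suppositions make the results upper limits.

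- Three diaries (pain assessment text): share of subjects losing one = 1 − (1 − q)³.
- Two diaries (timetable footnote): share = 1 − (1 − q)², because nothing is outstanding between T2 and T3.
- Subjects with no diary VAS = 40q, from N = 40.

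| q | Three diaries | Two diaries | No diary VAS, of 40 |
|---|---|---|---|
| 5% | 1 − 0.857 = 14.3% | 1 − 0.9025 = 9.8% | 2 |
| 10% | 1 − 0.729 = 27.1% | 1 − 0.81 = 19.0% | 4 |
| 15% | 1 − 0.614 = 38.6% | 1 − 0.7225 = 27.8% | 6 |

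**4. Precision, for illustration.** With 20 per arm, two-sided α of 0.05 (the plan does not state sidedness), 80% power and a normal approximation, the detectable difference is (1.960 + 0.842) × √(2/20) = 0.89 SD. With 10% of diaries lost evenly (18 per arm) it is 2.802 × √(2/18) = 0.93 SD. The loss of precision is modest.

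**The case against.** The strongest reply is that the loss is inferred, not stated. A disqualified subject continues treatment with the same provider, so could still bring the diary in. The bar on further data could mean no new measurements, with ratings written in week 1 counting as already collected. This stands in part: a reader might infer that every disqualified subject loses exactly one diary for good, and the documents do not support that. The PI may also withdraw a subject within the first seven days, before any diary is complete. What remains is that the plan describes no way to accept such a diary and does not say that it counts.

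Second, a reader might infer that the pain aim rests on the diaries alone. It does not quite: OHIP-14, given at every study visit, has a physical-pain dimension. That dimension is not a daily rating of the week after activation, so it does not replace the diary.

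Third, completion from memory is a risk and not planned practice. The instruction is to record each evening, and nothing permits otherwise. Equally, nothing verifies it: no dated receipt, reminder or completeness check at hand-in is described.

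Fourth, if diaries are lost for reasons unrelated to pain, the cost is mainly precision, which is small. That is fair. The documents do not show whether missed visits or late repairs relate to pain or to arm, so bias is possible but not demonstrated.

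**Conclusion.** The concern holds as a gap in the plan and a cheap improvement. Collection only at the next visit leaves 28-35 days (T0), 21-42 days (T1) and 14-42 days (T2, if issued) between the last entry and hand-in. Nothing provides for a diary finished before disqualification but still with the subject.

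The upper limits on subjects losing one diary are 14%, 27% and 39% with three diaries, or 10%, 19% and 28% with two. They rest wholly on the assumed 5%, 10% and 15% per interval and are not forecasts. The conflict over how many diaries are issued is in the documents and needs reconciling whatever the rate.

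The effect is confined to a secondary outcome of a pilot; the salivary biomarker outcome is untouched. The change is worth making because it is easy and because 20 subjects per arm leave little room to discard ratings already made.

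**What to change.** - **Orthodontic Pain Assessment:** ask for return of each diary on about day 8 by photograph of the page or pre-addressed envelope, record the date of receipt, and keep the next visit as a back-up.
- **Section V:** state that a diary completed before disqualification is collected and scored.
- **Timetable footnote and Orthodontic Pain Assessment:** reconcile the number of diaries issued.
- **Section VI:** add a sensitivity analysis of VAS that leaves out late-received diaries, with the cut-off fixed in advance (for example, received after day 14).

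The cost is protocol wording, a reminder, and up to three photographs or envelopes per subject. No extra appointment is needed, so the rule on scheduled visits is respected, and treatment is unchanged. The downside is a small added task for subjects. Early return shortens the possible recall period but does not prove that entries were made each evening, since all seven could still be filled in on day 8.

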- 4) The orthodontic treatment pain will be reduced in patients undergoing combined treatment with a vibration appliance compared to controls.

General Objectives

Few studies exist examining the effect of vibration appliances on the rate of orthodontic tooth movement in patients. Furthermore, there is a great need to better understand the biological mechanisms by which vibration treatment may enhance tooth movement. *The primary objective of this study is to identify potential factors involved in bone remodeling which may be regulated during fixed appliance treatment in conjunction with vibration therapy.*

Specific Aims

[figure not shown]
- 1) To determine if combined vibration-fixed appliance treatment alters the expression of specific bone remodeling factors in saliva compared to fixed orthodontic treatment alone.
- 2) To further elucidate the role of vibration treatment on the degree of tooth mobility during fixed appliance treatment compared to control.
- 3) To determine if combined vibration-fixed appliance treatment increases the speed of orthodontic tooth movement during the alignment phase of treatment.
- 4) To evaluate the role of vibration treatment in the control of pain in patients undergoing orthodontic treatment.

Study Design and Screening Procedures

Study Design: Randomized controlled clinical trial:

N=40 @ UCHC Orthodontic Clinic, enrolled pre-bonding

10 Randomized to each Arm

Screening & Recruitment Procedures

Approximately 600 patients begin treatment every year in the University of Connecticut Orthodontic Clinic. The pilot project aim is to recruit a total of 40 patients, with 20 male and 20 female subjects, equally divided between control and vibration groups (above).. Based on the projected starts, we anticipate meeting the recruitment goals during the first 12 months of the study.

Prospective subjects will be screened for this study after completing all the usual initial screening procedures for patients in the University of Connecticut Orthodontic Clinic with their appointed primary orthodontic provider. The primary orthodontic provider will determine if the adult patient is likely to qualify (pre-screen) for the study based on the inclusion/exclusion criteria. The initial clinical indicators of eligibility evaluated during the pre-screen are a healthy patient undergoing non-extraction treatment with good oral hygiene. Male and female subjects of all ethnicities will be included if between the ages of 15-35 years of age.

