	Have you felt tense because of problems with your teeth or mouth?	0.55
Physical Disability	Has your diet been unsatisfactory because of problems with your teeth or mouth?	0.52
	Have you had to interrupt meals because of problems with your teeth or mouth?	0.48
Psychological Disability	Have you found it difficult to relax because of problems with your teeth or mouth?	0.60
	Have you been a bit embarrassed because of problems with your teeth or mouth?	0.40
Social Disability	Have you been a bit irritable with other people because of problems with your teeth or mouth?	0.62
	Have you had difficulty doing your usual jobs because of problems with your teeth or mouth?	0.38
Handicap	Have you felt that life in general was less satisfying because of problems with your teeth or mouth?	0.59
	Have you been totally unable to function because of problems with your teeth or mouth?	0.41

Each question is answered on a 5-point scale:

0=never

1=hardly ever

2=occasionally

3=fairly often

4=very often

Individual scores are multiplied by the weights to give a subscale score for each category.

IV. Sample size and justification

Few studies exist evaluating salivary biomarkers during orthodontic tooth movement. Our primary outcome is changes in the expression of specific biomarkers of cellular activation and bone remodeling. No RCTs are currently available to predict treatment effects on biomarker expression. This study will serve as a pilot project with 40 patients total in 4 groups divided by gender and vibration/no-vibration treatment arms.

We estimate 600 patients in the target age range beginning orthodontic treatment at the University of Connecticut Orthodontic Clinic each year. We anticipate meeting our recruitment goal for this study.

V. Subject Participation

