(the study coordinator) will collect all tooth mobility measurements with the Periotest and means will be evaluated using non-parametric statistical analyses.

A Wilcoxon Rank Sum test for independent samples will be used to assess differences between groups for all the continuous variables with an $\alpha=0.05$ for irregularity index changes-Periotest measurements, VAS & OHIP-14 measures.

Salivary biomarker expression will be analyzed by ANOVA to assess differences between the four study groups at each time point. The study coordinator and principal investigator will perform statistical analyses.

VII. Timetable Table Timeline of Performance Goals:

Activity	Year 1-2014			Year 2-2015		
	X					
IRB, Staff training & preparation	X					
Subject Recruitment & Enrollment	X	X	X			
Final Assessments/Endpoints (17 weeks)				X		
Data Entry & Cleaning				X	X	X
Data analyses					X	X
Report writing						X

Expected Start Date: 2/1/2014

General Time Table

January 2014

Submit IRB for full board review

February 2014

Enrollment begins

Begin data collection for T0 time point in recruited subjects

August 2014

Initially recruited subjects complete study to final endpoint (T4)

June 2015

All consented subjects will have completed study

Data collection complete (N=20)

July 2015

Data analyses conducted

August 2015

Manuscript Preparation

➤ ***Expected Completion Date:*** August 2015

5) **Budget**

Patients will be responsible for covering the cost of orthodontic treatment in the University of Connecticut Orthodontics Clinic (either directly or with insurance). However, a deduction of \$400.00 on the standard orthodontic fees will be given to every patient enrolling in the research. The participants will receive this incentive in the form of \$100.00 at each research appointment completed until the maximum benefit is reached. If a participant is not compliant with the study protocol, he/she will be dismissed from the study and will not receive any further compensation. The same orthodontic procedures will be used for all subjects in this study regardless of study group.

Please see the attached budget detailing the study-specific costs.

6) **Dissemination**

The results of this research will be published in a peer-reviewed dental journal. In addition, this work is likely to be presented at national/international meetings.

References

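### The size is justified only by a pilot label, and the analysis plans tests without any vibration-versus-control estimate or confidence interval, so a non-significant result would say little

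*Combined protocol and SAP*

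**What the plan says.** Section IV (Sample size and justification) contains no calculation. It notes that "Few studies exist evaluating salivary biomarkers during orthodontic tooth movement" and that "No RCTs are currently available to predict treatment effects on biomarker expression", and concludes: "This study will serve as a pilot project with 40 patients total in 4 groups divided by gender and vibration/no-vibration treatment arms". Its only other argument is feasibility: "We anticipate meeting our recruitment goal for this study". It states no effect size, SD, power or target precision.

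The study design section gives the cell size ("10 Randomized to each Arm"), and section II confirms it within each sex ("10 for the vibration study group, 10 for the non-vibration control group").

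Section VI (Statistical/Data Analysis) names three things:

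- Cronbach's alpha for rater reliability of the irregularity measurements.
- Wilcoxon rank-sum tests between groups "with an $\alpha=0.05$ for irregularity index changes-Periotest measurements", and also for VAS and OHIP-14.
- For the primary outcome, an ANOVA of salivary biomarkers "to assess differences between the four study groups at each time point".

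For the biomarkers there is no significance level, no contrast for vibration and no statement of how sex or the baseline value enters. For no outcome is there a treatment-effect estimate, a confidence interval or a rule for reading a non-significant result.

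**The concern.** Section IV says the trial is small because treatment effects on these markers cannot yet be predicted. Section VI, followed as written, would not report what those effects turned out to be. The pilot rationale and the test-only analysis do not match.

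The choice of primary test adds to this. Aim 1 asks whether adding vibration alters marker expression compared with fixed treatment alone. A four-group ANOVA asks whether any of the four sex-by-arm means differ. A sex difference alone can make it significant, and a significant result does not say which factor was responsible. Its three numerator degrees of freedom also cost power against the one contrast of interest.

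At stake is what can be concluded at the end. With many markers and several visits, the planned biomarker output is a list of omnibus p-values. Small and moderate vibration effects would usually appear as non-significant, with no interval to show what the data still allow.

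**Working it through.** **The plan's own figure.** 4 cells x 10 = 40, which agrees across the study design section, section II and section IV. It cannot be reproduced as a power calculation because effect size, SD and power are not given. What 40 subjects can deliver is therefore worked out in SD units.

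**Inputs from the document.** 10 per sex-by-arm cell, so 20 v 20 by arm. There are 14 markers: 13 antibody targets plus CTX, listed under Salivary Biomarkers. There are three post-baseline visits (T1, T2, T3).

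**Assumptions.** Two-sided 0.05 (the plan gives no level for the ANOVA and no sidedness for the other tests); the same vibration effect d, in SD units, in both sexes; no sex effect; roughly normal data, perhaps after a log transformation; no dropout unless shown.

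**Step 1: power of the two comparisons.** With the effect split as +d/2 and -d/2 around the mean, the noncentrality is N x (d/2)². At d = 0.5 it is 40 x 0.0625 = 2.5. It is the same for both comparisons; only the degrees of freedom differ (3 and 36 for the four-group ANOVA, 1 and 38 for the 20 v 20 contrast).

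| True effect (SD) | Four-group ANOVA | Direct 20 v 20 contrast |
|---|---|---|
| 0.3 | 10% | 15% |
| 0.5 | 21% | 34% |
| 0.8 | 50% | 69% |
| 1.0 | 71% | 87% |
| Effect with 80% power | 1.10 SD | 0.91 SD |

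A true effect of 0.5 SD would be missed about 79% of the time by the planned ANOVA and about 66% of the time by the direct contrast. Section V disqualifies subjects for missed visit windows or late bracket repair. If that left 8 per cell (an illustration), the ANOVA would reach 80% power only at 1.25 SD.

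**Step 2: what an interval would show.** The 95% half-width for 20 v 20 is t(0.975, 36 df) x sqrt(2/20) = 2.028 x 0.316 = 0.64 SD.

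- Observed difference 0: -0.64 to +0.64 SD.
- Observed difference 0.3 SD: 0.3 - 0.64 = -0.34 to 0.3 + 0.64 = +0.94 SD.
- With 16 v 16, the half-width is 0.72 SD.

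On a log scale the upper limit around a null ratio is exp(0.64 x log-SD). The document gives no marker SD, so a range is assumed: 1.47 at log-SD 0.6, 1.67 at 0.8 and 1.90 at 1.0, with the reciprocals below 1.

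**Step 3: number of intervals.** 14 markers x 3 visits = 42. If vibration had no effect on any marker, 42 x 0.05 = 2.1 unadjusted 95% intervals would be expected to exclude no effect by chance.

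**The case against.** The strongest reply is that the document never sets out to estimate effects for a later trial. The Study Rationale and General Objectives speak of identifying factors, the hypotheses are directional, and the pilot label serves only to explain why there is no power calculation. That is correct. A reader might infer that the trial fails its stated pilot purpose, but no such purpose is written. What stands is the narrower mismatch between the reason given for the size and the output planned. Identifying which factors respond to vibration also needs the size and uncertainty of each effect.

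Other tempting readings go too far:

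- *A null result will be reported as no effect.* No text says so. It is a risk that the plan leaves open.
- *Nearly everything will be non-significant whatever the truth.* This is wrong for large effects. At 1.0 SD the power is 71% for the ANOVA and 87% for the direct contrast.
- *A null estimate would be compatible with large effects.* An estimate of exactly zero, with limits of ±0.64 SD, excludes 0.8 SD. A non-significant estimate of 0.3 SD would not.
- *The ANOVA cannot give estimates.* It produces cell means and a residual variance, from which a difference and its interval follow. The gap lies in what the plan commits to report.
- *The ANOVA is run at 0.05.* Section VI attaches that level only to the rank-tested outcomes.
- *No effect data exist.* Section IV says there are no RCTs and few studies on biomarkers, and the Background reports trial results on alignment.

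It can also be said that intervals could be added after data collection without touching the design. That is true, and it is why the change is cheap. Fixing the contrast, scale and adjustment beforehand still protects against choosing them after seeing 42 results.

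**Conclusion.** The point holds as a gap in planned analysis and reporting that should be closed. It does not show that the design is unsound. Section IV rests the size on a pilot label alone, and section VI commits to tests without a vibration estimate or interval. The primary test does not isolate vibration from sex and needs an effect of about 1.10 SD for 80% power, where a direct contrast on the same subjects needs about 0.91 SD.

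A non-significant result would be weak evidence: even a zero estimate leaves differences up to about 0.64 SD open in either direction. These figures rest on the assumptions listed with the calculation. Dropout would make them worse, and a baseline value that predicts follow-up would improve them. A sex effect would make the ANOVA reject more often, but not because of vibration. All figures take 40 as the total; the section VII timetable gives 20 at the end of data collection, which needs separate reconciliation.

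**What to change.** Rewrite the comparison paragraphs of section VI as follows.

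- **Biomarkers.** For each marker and each post-baseline visit, make the main output the vibration/control ratio with 95% CI, from a model on the log scale with arm, sex and the baseline value. Report the between-subject SD. This replaces the four-group omnibus test as the main result.
- **Irregularity, Periotest, VAS and OHIP-14.** Keep the rank-sum test and report the Hodges-Lehmann difference with 95% CI beside it.
- **Multiplicity.** State that 14 markers x 3 visits give 42 unadjusted, exploratory intervals, of which about 2 would exclude no effect by chance.
- **Interpretation.** State that p > 0.05 will be reported as inconclusive unless the interval excludes effects of interest, and name those effects beforehand where the investigators can.

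The cost is analysis wording only: no extra subjects, visits or assays. The downside is that null findings must be stated as inconclusive. The change does not make the trial large enough for moderate effects: 80% power at 0.5 SD would need about 63 per arm (normal approximation).
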